5.4.4.2 EQ-5D-5L-PSO

Open-label phase:

EQ-5D-5L-PSO dimensions, the index score and health on VAS score will be summarised by visit.

A shift table for the category for each of the EQ-5D-5L-PSO dimensions at visit 1 versus the category at visit 2 will be done.

Change and percent change in EQ-5D-5L-PSO index score and health on VAS score from visit 1 to visit 2 will be summarised.

Trial ID: LP0053-1004	Date: 15-JUL-2019	Version: 1.0 Page 25 of 177
-----------------------	-------------------	--------------------------------

Maintenance phase:

EQ-5D-5L-PSO dimensions, the index score and health on VAS score collected when the subject is not initiating, ending or in a relapse period will be summarised by visit and by treatment group.

EQ-5D-5L-PSO dimensions, the index score and health on VAS score collected when the subject is initiating a relapse period will be summarised by visit and visit intervals and by treatment group.

EQ-5D-5L-PSO dimensions, the index score and health on VAS score collected when the subject is ending a relapse period will be summarised by visit and visit intervals and by treatment group.

A shift table for the category for each of the EQ-5D-5L-PSO dimensions at start of relapse versus the category at end of relapse will also be done by visit for start of relapse and by treatment group.

Change and percent change in EQ-5D-5L-PSO index score and health on VAS score from start of relapse to end of relapse will be summarised by visit for start of relapse and by treatment group.

EQ-5D-5L-PSO dimensions, the index score and health on VAS score collected when the subject is in a relapse period, will be listed only.

See section [5.7](#) for details regarding changes as compared to the protocol.

More details for the tables and listings can be found in [Appendix I](#) and [Appendix II](#).

The index score will be calculated calculated according to:

<https://euroqol.org/eq-5d-instruments/eq-5d-5l-about/valuation-standard-value-sets/crosswalk-index-value-calculator/>.

The UK value sets will be used. In this way, each possible EQ-5D health state is assigned a weight representing the utility or value of that state, on a scale with a maximum value of 1, representing full health, and an anchor of 0, representing equivalent to being death. Values lower than 0 represent states regarded as worse than being death.

5.4.4.3 WPAI:PSO

The WPAI:PSO questionnaire will be presented by impairment percentages with high number indicating greater impairment. Four derived domains will be constructed from the WPAI:PSO questions (Q1-Q6) as described in [Table 6](#).

Table 6: Scoring of WPAI:PSO question 1-6

Impairment percentage	Score
Absenteeism	$Q2/(Q2+Q4)$
Presenteeism	$Q5/10$
Total work productivity impairment (TWPI)	$Q2/(Q2+Q4)+(1-Q2/(Q2+Q4))\times(Q5/10)$
Total activity impairment (TAI)	$Q6/10$

Open-label phase:

The WPAI:PSO scores will be summarised by visit.

Change and percent change in each WPAI:PSO questions from visit 1 to visit 2 will also be summarised.

Maintenance phase:

The WPAI:PSO scores will be summarised by visit, by treatment group and by whether the subject is on rescue IMP or not. As the WPAI:PSO questionnaire is based on experiences with psoriasis during the past 7 days, a subject will be summarised in the rescue IMP category if the subject has been on rescue IMP in at least one of the past 7 days prior to the visit.

WPAI:PSO scores collected at unscheduled visits will be listed only.

More details for the tables and listings can be found in [Appendix I](#) and [Appendix II](#).

5.4.4.4 Psoriasis Symptom Inventory

The total PSI score is calculated by summing the individual item score of each of the eight symptoms. If one question is left unanswered, this is scored 0, and the total score is calculated as usual. If two or more questions are left unanswered, no total score is calculated. The answers are scored as described in [Table 7](#). The total PSI score ranges from 0 (not at all severe psoriasis symptoms) to 32 (very severe psoriasis symptoms).

Table 7: Scoring of PSI questions

Answer	Score
Very severe	4

Answer	Score
Severe	3
Moderate	2
Mild	1
Not at all	0
Unanswered	0

Open-label phase:

The AUC for total PSI scores will be calculated. Change and percent change in total PSI score from visit 1 to visit 2 will also be summarised.

The AUC for the PSI total score will be calculated for each subject using the standard trapezoidal rule where trial day is used for the x-axis of the curve and total PSI score is used for the y-axis of the curve. The AUC will be normalised by dividing with the time period from visit 1 to visit 2. The normalisation converts the AUC to the original scale of the total PSI score.

Maintenance phase:

The AUC for the total PSI scores (from randomisation to 28 weeks after randomisation) will be calculated. The AUC for the total PSI score collected in time in remission and time in relapse, respectively, will be summarised by treatment group.

The AUC for the PSI total score for time in remission will be calculated for each subject by summing AUC over the time intervals where the subject is in remission. The AUC will be normalised by the total time the subject is in remission.

Likewise, the AUC for the PSI total score for time in relapse will be calculated for each subject by summing AUC over time intervals where the subject is in relapse. The AUC will be normalised by the total time the subject is in relapse. Missing assessment of the PSI total score in-between non-missing assessments in the maintenance phase will not be imputed, which corresponds to linear interpolation between non-missing assessments of the PSI total score.

Multiple imputation:

Missing DLQI total scores will be imputed using multiple imputation with 100 copies (seed=70309491). The imputation method and the imputation steps are the same as described for DLQI in section [5.4.4.1](#), however the imputation is done by week and not by visit.

Trial ID: LP0053-1004	Date: 15-JUL-2019	Version: 1.0 Page 28 of 177
-----------------------	-------------------	--------------------------------

Statistical analysis:

For each of the 100 complete data sets, the total PSI scores will be analysed using a Mixed effect Model Repeat Measurement (MMRM) with treatment group, week (from randomisation), interaction between treatment and week, relapse status, and maintenance baseline total PSI score as fixed factors and subject as random effect. Repeated measurements within subject is modelled using an unstructured variance structure. REML will be used for estimation.

The estimates and standard errors from the 100 analyses will be pooled into estimated least squares means for each treatment group and estimated treatment difference with associated standard errors using Rubin's rule to draw inference. From these pooled treatment estimates, the 95% CI for the treatment difference will be calculated. The p-value for treatment difference will be calculated using a two-tailed Student's t-test based on the pooled estimate. Pooled treatment estimates together with treatment difference, 95% CI and p-value will be presented by week. Furthermore, the pooled treatment estimates will be plotted by week.

Subjects are supposed to complete the PSI questionnaire on a weekly basis the first 28 weeks of the maintenance phase and the 2 last weeks of the maintenance phase (Week 54 to 56) which is only applicable for completers. However, during blind review of data, it is observed that subjects in general forget to complete the questionnaire the last 2 weeks which implies that limited data are available for this period. For this reason, the analysis of the PSI total score will be based on the first 28 weeks of the maintenance phase.

The analysis of PSI will be done for full analysis set.

More details for the tables and listings can be found in [Appendix I](#) and [Appendix II](#).

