6.1.4.3 Relapse between regular 4 week (scheduled) visits – less than one week to the next regular visit

If a relapse/exacerbation of psoriasis occurs within one week (7 days) prior to the next scheduled visit, the subject should attend the next scheduled visit and the procedure described in section 6.1.4.1 should be followed. For illustration, see [Figure 4](#) below.

Figure 4 Relapse between regular 4 week (scheduled) visits – less than one week to the next regular visit

Trial visits (initial open-label treatment phase and maintenance phase)

The total trial duration will be up to 64 weeks (including 8 weeks follow-up) and will include at least 15 regular visits.

All post-randomisation visits (Visits 3 to 15) should be performed within \pm 4 days of the scheduled time relative to Visit 2; if the visit is performed outside of the visit window, the investigator should record the reason in the subject's medical record. The same visit window (\pm 4 days) is applicable for the follow-up of any unscheduled visits due to relapse.

The maintenance IP will be dispensed at each regular visit (from Visit 1 to Visit 14) and used maintenance IP will be collected at the next regular visit (from Visit 2 to Visit 15). Rescue IP will either be dispensed at a regular visit and collected at the next regular visit, or be dispensed at an unscheduled visit and collected at a relapse follow-up visit 4 weeks later, as applicable. The number of cans to be dispensed depending on the different trial phases is specified in section 10.4. Subjects should not discontinue treatment themselves between the trial visits. This applies to both maintenance treatment and rescue treatment following relapse.

The DLQI and EQ-5D-5L-PSO questionnaires will be completed at each visit to the site.

In addition, the subjects will be asked to complete the WPAI:PSO at baseline (Visit 1), at randomisation (Visit 2/Week 4), after approximately 6 months (Visit 8/Week 28) and at the end of treatment (Visit 15/Week 56).

At baseline (Visit 1), subjects will be instructed on how to capture psoriasis symptoms in the eDiary (e.g. erythema, scaliness, itching, etc...) using the PSI.

At home, subjects will complete the PSI daily during the open-label treatment phase (starting at Visit 1), then weekly during the first 28 weeks of the maintenance phase (Weeks 4 to 28) and the 2 last weeks of the maintenance phase (Week 54 to 56 - only applicable for completers).

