8.13.4 Psoriasis symptom inventory (PSI)

The PSI, an eight-item measure to assess the severity of psoriasis symptoms will be completed by subjects daily during the initial open-label treatment phase (starting at Visit 1) and then weekly during the first 28 weeks of the maintenance phase (Weeks 4 to 32 (Visits 2 to 9)) and the 2 last weeks of the maintenance phase (Week 54 to 56 (Visits 14 to 15) - only applicable for completers).

The eight symptoms include itch, redness, scaling, burning, cracking, stinging, flaking and pain. 'Scaling' refers to the skin forming plates or scales that represent compacted desquamated layers of stratum corneum, which may then peel off; 'flaking' refers simply to loss of dry skin cells. Subjects rate the severity of each symptom on a 5-point Likert-type rating scale ranging from 0 (not at all) to 4 (very severe). Individual item scores are summed for a total score, which ranges from 0 to 32. The PSI will be administered as a 24-h recall version during the initial open-label treatment phase and as a 7-day recall version during the maintenance phase (the 7-day version was previously shown to provide results equivalent to 24-h recall version (22) (see [Appendix 10: Psoriasis Symptom Inventory \(PSI\) – 24 hours recall](#) and [Appendix 11: Psoriasis Symptom Inventory \(PSI\) – 7 days recall](#) respectively).

At baseline (Visit 1) the subject will complete this questionnaire in the eDiary while at the trial site. The subject will then subsequently fill this out while at home for all other timepoints/periods.

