SD: Standard deviation, Q1: 1st quartile, Q3: 3rd quartile, AUC: Area under the curve. AUC is calculated based on all the daily total PSI scores using the trapezoidal rule to approximate the area under and is normalised by the total number of days in the open-label phase.

Shell 45: <Change / Percent change> in total PSI score from start to end of open-label phase: open-label safety analysis set

Total PSI score from visit 1 to visit 2	Open-label safety analysis set (n=xxx)	Randomised subjects (n=xxx)	Not randomised subjects (n=xxx)
Number of subjects	xxx	xxx	xxx
Mean (SD)	xx.x (xx.x)	xx.x (xx.x)	xx.x (xx.x)
Median	xx.x	xx.x	xx.x
Q1;Q3	xx.x;xx.x	xx.x;xx.x	xx.x;xx.x
Min;Max	xx.x;xx.x	xx.x;xx.x	xx.x;xx.x

SD: Standard deviation, Q1: 1st quartile, Q3: 3rd quartile

Shell 46: Total PSI score for time on rescue medication and time in remission during the first 28 weeks of the maintenance phase: full analysis set

	LEO 90100 (n=xxx)	Vehicle (n=xxx)
Total PSI score (AUC)		
Time in remission		
Number of subjects	xxx	xxx
Mean (SD)	xx.x (xx.x)	xx.x (xx.x)
Median	xx.x	xx.x
Q1;Q3	xx.x;xx.x	xx.x;xx.x
Min;Max	xx.x;xx.x	xx.x;xx.x
Time in relapse		
Number of subjects	xxx	xxx
Mean (SD)	xx.x (xx.x)	xx.x (xx.x)
Median	xx.x	xx.x
Q1;Q3	xx.x;xx.x	xx.x;xx.x
Min;Max	xx.x;xx.x	xx.x;xx.x
Time in maintenance phase		
Number of subjects	xxx	xxx
Mean (SD)	xx.x (xx.x)	xx.x (xx.x)
Median	xx.x	xx.x
Q1;Q3	xx.x;xx.x	xx.x;xx.x
Min;Max	xx.x;xx.x	xx.x;xx.x

SD: Standard deviation, Q1:1st quartile, Q3: 3rd quartile, AUC: Area under the curve.

Average PSI score is calculated as area under the curve (AUC) over the time intervals on rescue medication

and the time intervals in remission for each subject. AUC is calculated based on all the weekly total PSI scores using the trapezoidal rule to approximate the area under and is normalised by the total number of days remission or relapse, respectively.

Shell 47: Statistical analysis of PSI: full analysis set

Weeks from randomisation	LEO 90100 vs. vehicle
Number of subjects randomised to LEO 90100	xxx
Number of subjects randomised to vehicle	xxx
Randomisation	
Estimated means	
LEO 90100	xx.xx
Vehicle	xx.xx
Treatment difference	xx.xx
95% CI	xx.xx-xx.xx
p-value	0.xxx or <0.001
Week 4	
Estimated means	
LEO 90100	
Vehicle	
Treatment difference	
95% CI	
p-value	
...	

continued...

Trial ID: LP0053-1004	Date: 15-JUL-2019	Version: 1.0
		Page 114 of 177

Weeks from randomisation	LEO 90100 vs. vehicle
Week 28	
Estimated means	
LEO 90100	
Vehicle	

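### The PSI area under the curve is divided by the whole period although it covers only the time between the first and last score, so uncovered time at the ends counts as a score of zero in descriptive Tables 2-87 and 2-90

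*SAP*

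**What the plan says.** SAP 5.4.4.4 sets the numerator: "The AUC for the PSI total score will be calculated for each subject using the standard trapezoidal rule". The divisors are whole periods.

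- **Open-label phase:** "The AUC will be normalised by dividing with the time period from visit 1 to visit 2". The Shell 44 footnote agrees in substance: the area "is normalised by the total number of days in the open-label phase". The SAP adds that this step puts the result back on the PSI score scale.
- **Maintenance phase:** "The AUC will be normalised by the total time the subject is in remission", and likewise for relapse. The Shell 46 footnote repeats it: the area "is normalised by the total number of days remission or relapse, respectively".

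Gaps between two non-missing scores are bridged by linear interpolation. The SAP gives no rule for time before the first or after the last score, for a weekly trapezoid that crosses the start or end of a relapse, or for a relapse with no score. The maintenance area runs from randomisation to 28 weeks. The remission and relapse divisors are limited to those 28 weeks only by the titles of Table 2-90 and Shell 46.

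The protocol gives two end dates for the weekly PSI. Section 6.1.4.3 (trial visits) has "then weekly during the first 28 weeks of the maintenance phase (Weeks 4 to 28"), and section 8.13.4 has "weekly during the first 28 weeks of the maintenance phase (Weeks 4 to 32 (Visits 2 to 9")).

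**The concern.** A mean obtained as area divided by time is on the score scale only if both refer to the same time. Here the area ends with the last entry while the divisor runs on. A diary that stops while the subject is still in the period is then scored as freedom from symptoms, and the reported mean reflects diary completion as well as disease.

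Nothing else in the plan repairs this. The multiple imputation refers back to the DLQI steps, which apply to withdrawn subjects and feed the repeated-measures model. The SAP does not link it to the area under the curve, and it describes no imputation for the open-label phase.

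The tables at stake are 2-87 (open-label PSI, randomised beside non-randomised subjects) and 2-90 (PSI in remission and in relapse, by arm). SAP 5.7 drops the summaries over time in favour of these areas, and Table 2-90 is the only PSI table split by remission and relapse.

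**Working it through.** The documents give no figure to reproduce, but they do state a property that can be tested: that the normalised area is on the PSI scale.

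**Inputs from the documents.** Open-label period 28 days with daily scores; maintenance window 28 weeks = 196 days with weekly scores; PSI total from 0 to 32; rescue treatment of a relapse 28 days; 4 to 8 relapses per year (Protocol 11.1). **Assumptions:** the two score profiles and the days on which the diary stops.

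**Open-label phase.** Reported mean = area to the last score / 28. Profile A is a constant 12 (true mean 12). Profile B falls linearly from 16 to 4 (true mean 10).

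The property holds for a complete diary (12.00 and 10.00) and for an interior gap on days 8 to 20 (again 12.00 and 10.00). For a last score on day 21:

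- A: 12 × 21 / 28 = 9.00, or 75% of the truth.
- B: the score on day 21 is 16 − 12 × 21/28 = 7. The area is 21 × (16 + 7)/2 = 241.5, and 241.5/28 = 8.62, or 86% of the truth.

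| Last score | A, area/28 | A, area/covered days | B, area/28 | B, area/covered days |
|---|---|---|---|---|
| Day 7 | 3.00 (25%) | 12.00 | 3.62 (36%) | 14.50 (+45%) |
| Day 14 | 6.00 (50%) | 12.00 | 6.50 (65%) | 13.00 (+30%) |
| Day 21 | 9.00 (75%) | 12.00 | 8.62 (86%) | 11.50 (+15%) |
| Day 24 | 10.29 (86%) | 12.00 | 9.31 (93%) | 10.86 (+9%) |
| Day 27 | 11.57 (96%) | 12.00 | 9.85 (98%) | 10.21 (+2%) |

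The planned mean is too low unless every unobserved score is 0. Dividing by covered days is exact for a constant score and too high for a falling one.

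**Remission and relapse, complete diary.** The share of each state's time that lies under the curve depends on how boundary trapezoids are treated.

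- *Split at the boundary by interpolation:* 100% of both states.
- *Only trapezoids wholly inside a period:* for a relapse on days 31 to 59, the weekly scores on days 35 to 56 cover 21 of 28 days (75%). Remission is covered for 28 + 133 = 161 of 168 days (96%). Simulating 4,000 subjects at each rate with exponential waiting times gives about 74–75% of relapse time, against 92%, 88% and 85% of remission time at 4, 6 and 8 relapses per year.

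**Remission and relapse, diary stopped at week 20 of 28, one 4-week relapse (so 24 weeks of remission).**

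| Relapse starts | Remission covered | Relapse covered |
|---|---|---|
| Week 4 or 14 | 16/24 = 67% | 4/4 = 100% |
| Week 18 | 18/24 = 75% | 2/4 = 50% |
| Week 22 | 20/24 = 83% | 0/4 = 0% |

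Simulated at 4 relapses per year with boundary splitting, the same stop gives mean coverage of 72% in remission and 68% in relapse. The relapse figure becomes 76% when relapse time with no score at all is left out. Relapse was the more diluted state in 50% of subjects and the less diluted in 50%.

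**Window.** If the remission and relapse divisors ran over 52 weeks while the area stopped at 28, the scale factor would be 28/52 = 0.54. If weekly entries ended at Week 28 of the trial (24 weeks after randomisation), coverage would be 24/28 = 86%.

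**The case against.** **Limited reach.** The areas are descriptive, untested and outside the multiplicity hierarchy. Tables 2-88 and 2-89 give the Visit 1 to Visit 2 change, and Table 2-91 carries the comparison between arms by week. This stands: no inferential PSI result changes.

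**No evidence of early stopping in the periods used.** A reader might take the SAP's remark that "subjects in general forget to complete the questionnaire the last 2 weeks" as proof. It concerns Weeks 54 to 56, which the analysis drops. The Visit 1 score is entered on site, sites review diary data, and a withdrawn subject's maintenance phase ends at last exposure (SAP 5.1), so that divisor shrinks too. What remains is a subject who stops the diary while still in the period. How often that happens is unknown.

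**Relapse against remission.** A reader might infer that relapse means are always pulled down more because relapses are short. That needs whole-interval trapezoids, which the SAP does not prescribe, and under that reading the larger relapse loss appears even with a complete diary. With boundary splitting the direction depends on when the diary stops.

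**Week 28 or Week 32.** A reader might infer a 14% loss for every subject. That rests on one parenthesis in Protocol 6.1.4.3, which conflicts with the 28 weeks in its own sentence, with 8.13.4, with the visit schedule in 8.1 and with the SAP. It is a discrepancy to reconcile, not a demonstrated bias.

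**The remedy is also biased.** This stands. On profile B with a stop at day 21, covered days give +15% where the plan gives −14%.

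**Conclusion.** The rule is wrong as written, and this is more than missing detail: the SAP names the divisor, and that divisor does not return the PSI scale when scores fail to span the period. The reported mean is too low whenever entries stop before the period ends, unless the unseen scores are all 0. For a stop at day 21 of 28 it is 75% of the truth with a constant score and 86% with an assumed fall from 16 to 4. Complete diaries and interior gaps are unaffected.

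In maintenance the size and direction of the loss can differ between relapse and remission. They turn on rules the SAP leaves open, so no general direction can be claimed. The effect is confined to Tables 2-87 and 2-90. The repeated-measures comparison of PSI between arms does not use the area and is not affected. The percentages rest on assumed profiles and stop days, since the documents report no diary completion for these periods.

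**What to change.** In SAP 5.4.4.4 and the footnotes of Shells 44 and 46:

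1. Divide each area by the days it covers, not by the whole period.
2. Split weekly trapezoids at relapse boundaries by linear interpolation.
3. Treat a period with no scored time as missing, not as 0.
4. State in the SAP text the limit to the first 28 weeks for remission and relapse time that the Shell 46 title implies.
5. Set a minimum coverage for inclusion before unblinding, and report scored days per period and arm. The threshold should be strict in the open-label phase, where subjects are expected to improve: on the falling profile the covered-time mean is still 9% high at day 24 (24/28 = 86% coverage) and 2% high at day 27 (96%). The documents do not determine a value.
6. Reconcile the PSI end date in Protocol 6.1.4.3 with 8.13.4.

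The cost is SAP and shell wording and a small program change; no new data are needed. The price is that subjects below the threshold drop out of these two tables, and some upward bias remains for improving subjects who stop early.

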5.4.4.5 Subject's Global Assessment of Disease Severity (SGA)

Open-label phase:

Subject's global assessment of disease severity (SGA) will be summarised by visit. A shift table for categories of subject's global assessment of disease severity at visit 1 versus the category at visit 2 will also be done.

Maintenance phase:

SGA collected when the subject is not initiating, ending or in a relapse period will be summarised by visit and by treatment.

Trial ID: LP0053-1004	Date: 15-JUL-2019	Version: 1.0 Page 29 of 177
-----------------------	-------------------	--------------------------------

SGA collected when the subject is initiating a relapse period, will be summarised by visit and visit intervals and by treatment.

SGA collected when the subject is ending a relapse period will be summarised by visit and visit intervals and by treatment group.

A shift table for categories of SGA at start of relapse versus the category at end of relapse will also be done by visit for start of relapse and by treatment group.

SGA collected when the subject is in a relapse period will be listed only.

More details for the tables and listings can be found in [Appendix I](#) and [Appendix II](#).

